### 1.3.2 Exploratory research question (if applicable)

Exploratory objectives include but are not restricted to following research questions:

- i. Are there any group differences in change of ESAS score other than pain?
- ii. What is the Patient Global Impression of Change in the two groups?
- iii. Is there a difference between SC and IV group in morphine concentration in steady state\*?  
(\*>24 hours after start of infusion and >2 hours since last bolus dose)
- iv. Is there a relationship between BMI and pharmacokinetic analyzes in the SC group?
- v. How does respiration frequency (RF) and oxygen saturation change during the intervention?  
Are there any differences between the SC and IV group?
- vi. What is the change in opioid side effect score in the two groups at 0, 24 and 48 hours
- vii. What is the change in opioid dose (in OME) from start of titration to 48 hours
- viii. What is the change in opioid dose (in OME) during follow up period
- ix. What are the complications to SC line and IV line
- x. What is the study population survival censored at 4 weeks

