## STATISTICAL ANALYSIS PLAN for SIM-study

---

Time	Screening Period	Treatment Period		
	Within 24 hours of treatment	Baseline/start of treatment Between 11 am and 3 pm	12, 24, 36, and 48 +/- 2 hours	24 +/- 2; 48 +/- 2 hours
Inclusion/exclusion Evaluation	X			
Height, Weight	X			
Medical History	X			
Prior analgesic treatment	X			
Current medication	X			
Vital signs		X	X	
ESAS-revised		X	X	
EORTC QLQ-C30		X		X(at 48 +/- 2 hours)
EAPC basic data set	X			
Opioid side effects		X		X
Patient Global Impression of Change				X (at 48 +/- 2 hours)
Blood samples 	X			
Treatment administration/dispensation		X	X	
Adverse event		X	X	X
Clinician's decision to continue ongoing treatment or to change treatment				X
Record of concomitant medication		X	X	X
Morphine dose		X	X	X
Hospitalization				
Survival				
Complications to IV line				
Need for switch SC to IV				
Reason for withdrawal				

1. Blood pressure, pulse, temperature, sedation level, respiratory rate

2. CRP, Hb, WBC (incl. differential counting), PLT, Na, K, Ca, creatinine, ASAT, ALP, γGT, INR, albumin, bilirubin

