### 3.3 Withdrawal/Follow-up

The status of eligible and randomized patients at trial end will be tabulated by treatment group according to:

- completed intervention and assessments.

- completed assessments but not intervention.
- completed intervention but not assessments.
- withdrew consent.
- lost to follow-up.

Time from randomization to treatment discontinuation and time from randomization to withdrawal/lost to follow-up will be presented in the CONSORT flow diagram.

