### 3.5 Analysis Populations

The enrolled set will include all patients who have provided informed consent and have been included in the study database.

**The Full Analysis Set (FAS)** will be defined as all patients randomly assigned to a treatment group regardless of whether they received any study treatment after randomization.

**The Safety Analysis Set (SAS)** will include all patients that receive any study treatment after randomization.

**The Per Protocol (PP) population** will include all randomized patients who meet the study eligibility criteria, and complete the study according to protocol with no major protocol deviations affecting the treatment efficacy.

**The intention to treat (ITT) population** will include all patients who were randomly assigned to a treatment group, regardless of whether they complete the treatment as planned: Main outcomes will be analyzed based on intention to treat principle. Supplemental PP analyses will be based on patients who completed the 48-hour double blind period.

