#### **4.1.4 Opioid side effect score**

A questionnaire used to rate the intensity of 10 common symptoms experienced when on opioid treatment, including nausea, vomiting, constipation, drowsiness, disorientation, hallucinations, and spasticity on an 11-point numeric rating scale mimicking the NRS scale will be used (Fallon et al., 2022)

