### 4.6.6 Missing Data

All patients with at least one measurement will be included in the analysis of secondary outcomes (b, c, and d), as the linear mixed model includes all available information, also from dropouts.

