## **5 Safety Analyses**

The number (and percentage) of patients experiencing each AE/SAE will be presented for each treatment group categorized by severity. For each patient, only the maximum severity experienced of each type of AE will be displayed. The number (and percentage) of occurrences of each AE/SAE will also be presented for each treatment arm.

The Data Monitoring and Safety Committee (DMSC) will be informed of serious adverse events. The committee will if necessary, make decisions about terminating the trial before completed inclusion.

Study-specific safety measurement during intervention period:

Repeated measurement of saturation (every 12 hours), sedation level and respiration frequency (every 2 hour and after each bolus dose) will be assessed by linear mixed models mirroring the approach used for the analysis of secondary outcome c).

Opioid side effects score, mean (SD) at 24 and 48 hours will be presented for each treatment group and compared by an independent samples t-test

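### The 24 h and 48 h opioid side-effect scores are compared by separate t-tests that leave out the baseline score, and at 48 h every patient without a 48 h score; a baseline-adjusted mixed model would be more precise and less exposed to dropout

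*SAP*

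**What the plan says.** Section 5 (Safety Analyses) sets the method for this score: "Opioid side effects score, mean (SD) at 24 and 48 hours will be presented for each treatment group and compared by an independent samples t-test". It gives no baseline term, change contrast or missing-data rule.

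Other parts of the SAP bear on this:
- Question vi in section 1.3.2 reads "What is the change in opioid side effect score in the two groups at 0, 24 and 48 hours". Table 1 schedules "Opioid side effects" at baseline, 24 h and 48 h, so the baseline score is in hand.
- The sentence in section 5 just before the t-tests says that saturation, sedation level and respiration frequency "will be assessed by linear mixed models mirroring the approach used for the analysis of secondary outcome c".
- Section 3.5 defines a Safety Analysis Set that "will include all patients that receive any study treatment after randomization".
- Section 4.6.6 says "All patients with at least one measurement will be included in the analysis of secondary outcomes (b, c, and d"; the side-effect score is not among these. Sections 4.4.2, 4.5.5 and 4.7.6 deal with the primary outcome, outcome b and the bolus episodes.
- Section 4.1.4 describes the instrument as "A questionnaire used to rate the intensity of 10 common symptoms experienced when on opioid treatment". It gives neither an SD nor a rule for combining the items.
- Section 3.3 has a category for patients who "completed assessments but not intervention", so stopping treatment does not by itself mean that the score is missing.

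**The concern.** A two-sample t-test on the 48 h level uses one of the three scores that each patient may have. If a patient's baseline score predicts the later one, leaving it out wastes information, and the comparison of levels does not address the stated question about change.

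The 48 h test also rests on patients with a 48 h score only. A patient with scores at 0 h and 24 h but none at 48 h contributes to the 24 h test and then disappears. In a trial of about 30 per arm, a safety comparison made less precise in this way is more likely to miss a real difference between routes. If the missing patients differ between routes in their side effects, the 48 h difference is also shifted.

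**Working it through.** **Inputs from the SAP.** 30 patients per arm and a 25% dropout allowance (section 4.9); scores at 0, 24 and 48 h (Table 1). The SAP gives no figure for this score, so there is none to reproduce. The sample size in 4.9 does reproduce: for a 12 h difference, SD 12 h and two-sided 5%, noncentral-t power is 0.8997 at 22 per arm and 0.9125 at 23, so 23 is the exact answer. That 25% is an allowance for the primary outcome and is borrowed here only as a loss rate.

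**Assumptions.** Normal scores with SD 1 at each visit (results are therefore in SD units) and equal correlation r = 0.5 or 0.7 between any two visits. Paired results below are for r = 0.5 / 0.7.

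**Step 1: precision with complete data.**
- t-test: SE = √(2/30) = 0.258.
- Adjusted for the 0 h score: SE = √(2(1 − r²)/30). For r = 0.5, √(2 × 0.75/30) = 0.224. For r = 0.7, √(2 × 0.51/30) = 0.184.
- Simulation agrees: 0.25 to 0.26 for the t-test, against 0.22 / 0.18 to 0.19.
- The same formulas hold at 24 h.
- A model of all three visits that lets the arms differ freely at baseline gives 0.25 to 0.26 in simulation, no better than the t-test. The gain comes from adjusting for baseline.

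**Step 2: precision with 25% random loss at 48 h** (7.5 of 30, taken as 8, leaving 22 per arm).
- t-test: √(2/22) = 0.302.
- Residual variance of the 48 h score given the 0 h score: v0 = 1 − r² = 0.75 / 0.51. Given the 0 h and 24 h scores: v2 = 1 − 2r²/(1 + r) = 0.667 / 0.424.
- Adjusted model: SE = √(2[v2/22 + (v0 − v2)/30]) = 0.257 / 0.210. Simulation gives 0.26 / 0.21 to 0.22.
- Neither method is biased here.

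**Step 3: bias if loss follows the 24 h score.** Suppose the share p with the highest 24 h scores in an arm has no 48 h score. The remaining 48 h mean falls by r × L(p), where L(p) = φ(z)/(1 − p) and z is the (1 − p) normal quantile. The bias in the route difference is r × [L(p1) − L(p2)], in favour of the arm losing more.

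| Loss by arm | L(p1) − L(p2) | Bias of t-test, r = 0.5 / 0.7 |
|---|---|---|
| 10% v 5% | 0.195 − 0.109 = 0.086 | 0.04 / 0.06 SD |
| 30% v 20% | 0.497 − 0.350 = 0.147 | 0.07 / 0.10 SD |
| 40% v 10% (extreme) | 0.644 − 0.195 = 0.449 | 0.22 / 0.31 SD |
| equal | 0 | 0 |

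Strict removal of the top scorers is the worst form of this mechanism. With probabilistic stopping at 30% v 20%, the bias is 0.04 / 0.06 SD at log-odds 1 per SD of score and 0.06 / 0.08 SD at log-odds 2. In all these cases the adjusted model gives about 0.00. Against a standard error of about 0.30, 0.07 to 0.10 SD is a quarter to a third of one standard error.

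**Step 4: where the model does not rescue the estimate.** If loss follows the unseen 48 h score (30% v 20%, top scorers), the t-test is off by 0.15 / 0.15 SD and the model by 0.12 / 0.08 SD. If the patients with the highest 24 h scores leave before 24 h, the 24 h t-test is off by 0.14 / 0.14 SD and a model with only their 0 h score by 0.12 / 0.08 SD.

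**The case against.** The strongest reply is that the t-tests are pre-specified comparisons of randomised arms and are unbiased under equal or random loss. Question vi can be read as descriptive. The neighbouring measures are recorded far more often (every 2 hours and after each bolus, or every 12 hours), so a different method for a score with two post-baseline visits is no contradiction. Unequal stopping would show in the table of adverse events leading to withdrawal (section 5.1). A mixed model also implicitly estimates scores for patients who left or died, which is a different quantity and not plainly a better one.

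Most of this stands. The SAP is not inconsistent here; it has chosen a weaker method than its own data allow. None of the reply meets the precision point, which holds whatever the dropout pattern.

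A reader might infer that the 48 h comparison will favour the route with more stopping. The document does not support that. The bias needs stopping that follows side effects, differs by route and leaves the 48 h score missing. The SAP states none of these, and section 3.3 allows for patients who are assessed after stopping. Nor should false-positive rates be pressed: strict top-score loss at 30% v 20% gives 6.5% / 8.8%, but the same rule with equal loss and no bias already gives 5.9% / 7.1%. Probabilistic stopping at 30% v 20% gives 5.3% to 5.8%.

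**Conclusion.** The point holds as a matter of efficiency and, conditionally, of small bias. Ignoring the baseline score leaves the standard error of the 48 h difference at about 0.26 SD instead of 0.22 or 0.18 SD with complete data, and at 0.30 instead of 0.26 or 0.21 SD with 25% random loss. This rests on assumed correlations of 0.5 and 0.7, and the gain shrinks towards nothing as the correlation falls towards zero.

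Under the three conditions on stopping, the added bias is about 0.05 to 0.10 SD at 30% v 20% loss. It runs towards zero if the route with more stopping has the higher scores and away from zero if it has the lower ones. The 24 h test is not affected by patients who leave after 24 h.

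The score is exploratory and outside the decision rule in section 2.4.3, so the primary conclusion does not change. This is worth considering, not a defect that must be repaired.

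**What to change.** In section 5, replace the two t-tests by a linear mixed model of the 24 h and 48 h scores with visit (categorical), group, group-by-visit and the 0 h score as covariate, and an unstructured covariance. Use all Safety Analysis Set patients with a 0 h score and at least one post-baseline score. An equivalent choice is to model the 0, 24 and 48 h scores with a common baseline mean for the two arms, using all patients with at least one score. A model that allows a free baseline difference should be avoided, because with complete data it gains nothing over the t-test. Report the 24 h and 48 h route differences with 95% confidence intervals, and tabulate missing scores at each visit by arm with reasons. State whether the model is fitted to a combined score or to each symptom.

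The cost is SAP wording only, since the scores are already collected. The drawback is reliance on missingness at random given the earlier scores: bias is only partly corrected if loss follows the unseen 48 h score or happens before 24 h. The table of missing scores lets a reader judge this.

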### **5.1 Adverse Events**

In the study population declining function, development of cachexia, increasing symptoms, worsening of laboratory results (including blood cells, inflammatory markers, measures of organ function, electrolytes), re-hospitalization, and even death are expected in the course of the disease. Such events will be recorded by the investigator as disease-related events. Such disease-related events will not be classified and handled as AE/SAE even if the event meets the definition of an SAE. If events are of greater intensity, frequency or duration than expected for the individual patient, the investigator considers there is a reasonable possibility that the event is related to the intervention, the event will be recorded as an AE/SAE.

The intensity of the adverse event will be classified as Mild / Moderate / Severe according to Common Terminology Criteria for Adverse Events version 4.0 (CTCAE).

The number (and percentage) of subjects with any AE leading to study drug withdrawal will be summarized by treatment group. The number of events and number (and percentage) of subjects with adverse events by system organ class (SOC) and preferred term (PT) will be summarized by treatment group, overall, for severe AEs and for AEs leading to study discontinuation. In addition, a summary table of AEs reported by  $\geq 20\%$  of all patients will be presented by SOC and PT. A detailed patient narrative will be given for any serious adverse event in the clinical study report in addition to listing. Sub-tabulations by diagnosis will also be presented.

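### Deaths and re-hospitalisations judged disease-related have no planned comparison by route, because every by-arm event output in SAP section 5 is limited to AEs and SAEs

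*SAP*

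**What the plan says.** Section 5.1 lists kinds of deterioration that the trial expects to see and ends the list with the most serious: "re-hospitalization, and even death are expected in the course of the disease". On recording, it says: "Such events will be recorded by the investigator as disease-related events". On status, it says: "Such disease-related events will not be classified and handled as AE/SAE even if the event meets the definition of an SAE".

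An exception returns an event to AE/SAE status. Its first condition is that the event is more severe, more frequent or longer-lasting than anticipated, and the text runs straight on into the second: "than expected for the individual patient, the investigator considers there is a reasonable possibility that the event is related to the intervention". No conjunction joins the two conditions.

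The outputs are defined on the AE/SAE class. Section 5 says: "The number (and percentage) of patients experiencing each AE/SAE will be presented for each treatment group categorized by severity". The counts of occurrences in section 5, and the tables by system organ class and preferred term in section 5.1, use the same class. Narratives and the listing cover SAEs. On oversight, section 5 says: "The Data Monitoring and Safety Committee (DMSC) will be informed of serious adverse events".

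Survival appears as the last exploratory question in section 1.3.2: "What is the study population survival censored at 4 weeks". Table 1 has rows for hospitalisation and survival.

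**The concern.** The plan creates a class of events that can meet the SAE definition but stand outside AE/SAE, and then defines every event output on AE/SAE. Whether a given death enters a by-arm table depends on the investigator's view of that one patient.

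That view is a weak filter here. Both arms receive morphine, and in advanced cancer an opioid-related deterioration can resemble progression of the disease. A judgement on one patient cannot show that such events are more frequent in one arm. Randomisation can, because a count of all deaths by allocated arm needs no attribution. After the first 48 hours the study is open label (section 2.1), so attribution of later events can also be influenced by knowledge of the route.

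At stake is whether the trial's report can answer a simple question: how many patients died or were re-hospitalised in each arm?

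**Working it through.** The SAP states no figure on this point, so there is none to reproduce. The check is to trace each planned output and ask whether a death or re-hospitalisation judged disease-related would appear in it by arm.

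| Output | SAP section | Covers such an event by arm? |
|---|---|---|
| Patients and occurrences by severity | 5 | No, AE/SAE only |
| Events by organ class and preferred term, severe events, events leading to drug withdrawal or study discontinuation, events in at least 20% of patients | 5.1 | No, AEs only |
| Narratives and listing | 5.1 | No, SAEs only |
| Status at trial end | 3.3 | No, five categories, none for death |
| Survival to four weeks | 1.3.2, item x | No arm comparison stated |
| Time-to-event methods | 4.7 | No, response to bolus doses only |
| Saturation, sedation, respiration, side-effect score | 5 | By arm, but measurements |
| Laboratory values, vital signs | 5.2, 5.3 | By arm, but measurements |
| Pain, other ESAS items, QLQ-C30, global impression of change | 4.6, 1.3.2, 4.1.3, 4.1.5 | By arm, but patient-reported scores |

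No row gives a by-arm count of these events. Section 4.8 makes any unspecified analysis exploratory and asks for a separate analysis plan, so a by-arm comparison of deaths is not covered elsewhere by default.

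**The exception sentence.** If both conditions are needed, an event suspected to be related but no worse than expected stays out of AE/SAE. If either suffices, it comes in, and so does an event that is worse than expected but not suspected to be related. The two readings give different SAE counts. Under both, the decision rests on the individual patient, so repairing the sentence does not close the gap.

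**Illustration of scale.** The only input from the SAP is 30 patients per arm (section 4.9). The death risks and the share s of deaths judged disease-related are assumptions, with s taken as equal in both arms.

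Excess deaths visible in the AE/SAE tables = 30 × (p2 − p1) × (1 − s)

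| Assumed four-week risks | All deaths per arm | Full excess | s = 50% | s = 90% | s = 100% |
|---|---|---|---|---|---|
| 10% v 20% | 3 v 6 | 3 | 1.5 | 0.3 | 0 |
| 10% v 30% | 3 v 9 | 6 | 3 | 0.6 | 0 |
| 20% v 40% | 6 v 12 | 6 | 3 | 0.6 | 0 |

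Even with every death counted, power to detect these differences at 30 per arm is about 0.19, 0.49 and 0.39 respectively. A by-arm table would therefore be descriptive.

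**The case against.** The strongest reply is that much is already compared by arm without anyone's attribution. Sedation, respiration and saturation, the measurements closest to opioid harm, are modelled by group, and symptom scores and laboratory values are also presented by group. This stands. A reader might infer that nothing listed in section 5.1 is compared by route; that is not so for worsening symptoms or laboratory results. Laboratory values are the weaker part, because Table 1 marks blood samples only at screening. None of these measurements counts a death or a re-hospitalisation.

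A reader might also infer that the DMSC is kept from seeing deaths attributed to disease. The documents do not support that. Section 5 says the committee is told of serious adverse events, but not that it is told of nothing else. Section 2.6 lets it recommend stopping for any safety concern. The protocol or a charter, neither shown, may give it more. What stands is that nothing in this SAP sends those deaths to the committee.

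The survival question may simply be loosely worded. Asking about the study population does not forbid a split by arm, and other items in the list also omit a group comparison. That is fair, but several items do name the groups, and survival has no method anywhere in the SAP.

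A four-week comparison is also not a clean comparison of routes. Section 4.5 allows conversion from SC to IV in follow-up. It remains a randomised comparison of initial allocation and should be labelled as such.

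Finally, striking splits can be invented. With 30 per arm, 8 deaths split 7 v 1 give a two-sided Fisher p of 0.052, and 9 split 8 v 1 give 0.026. But 8 split 6 v 2 give 0.25, and 5 v 3 give 0.71. The SAP supplies no death rate, so none of these is evidence of how large the problem is.

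**Conclusion.** The point holds for deaths, re-hospitalisations and other SAE-definition events that the investigator judges disease-related. No planned output compares them by allocated route independently of that judgement. The events are not lost: they are recorded, and survival is a listed data item. What is missing is a planned presentation by arm.

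The size cannot be stated. It depends on the death risk and on the share attributed to disease, and the SAP gives neither. In the illustration, with 90% attributed to disease, an excess of 6 deaths shows as 0.6 in the AE/SAE tables.

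The conclusion rests on the SAP alone. An unseen protocol or charter could widen what the DMSC receives, but the by-arm tables are for the SAP to specify. The missing conjunction in section 5.1 may be a typing slip or a loss in text extraction, and is a secondary point. The change is a cheap improvement to safety reporting. It does not call the primary analysis into question.

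**What to change.** Leave the reporting rule in section 5.1 as it is, and make these changes:

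- **Section 5:** add a descriptive by-arm table and listing of all deaths, re-hospitalisations and other events meeting the SAE definition, regardless of attribution. Show the 48-hour blinded period and the four-week open-label follow-up separately, with a note that routes may be switched in follow-up.
- **Survival:** report four-week survival by allocated arm and name the method.
- **DMSC:** state in section 5 that the committee also receives these counts, unless the protocol or charter already provides for it.
- **Section 5.1:** reconcile the exception sentence with the protocol so that it is clear whether both conditions or only one is needed.

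The cost is one or two tables from data already recorded, a listing, and a line in the DMSC report. The downside is a longer table with many expected events and little power at 30 per arm, so it should be read as description and not as a test.
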